9.2 Secondary study parameter(s)

Analyses for the secondary study parameters are descriptive. Clinical and follow-up data for pediatric hospitalized COVID and MIS-C patients have been collected since the beginning of the pandemic. Data collection is ongoing. Using R and the Castor API, we continuously report our findings online, plotting an epidemic curve comparing COVID and MIS-C, and analyze baseline characteristics, clinical course and laboratory values, using Kruskal-Wallis, Chi-square or Fisher Exact depending on the variables (see our website www.covidkids.nl/scientific-dashboard). We will expand these analyses to include laboratory values, treatment and long-term outcome (including patient reported outcomes measures). We will do multi-variate analyses to determine which factors are independent predictors of outcome.

10. ETHICAL CONSIDERATIONS

10.1 Regulation statement

This study is subject to the Medical Research Involving Human Subjects Act (WMO). This study will be conducted according to the principles of the Declaration of Helsinki (version 2013, 19-10-2013), and in accordance with the Medical Research Involving Human Subjects Act (WMO), the General Data Protection Regulation (AVG) the Dutch Act on implementation of the General Data Protection Regulation (uitvoeringswet AVG), the Code of Conduct for Responsible Use of Human Tissue (Gedragscode Goed gebruik van lichaamsmateriaal) and other guidelines, regulations and acts. We will comply with the principles enshrined in the Council of Europe Convention on human rights and biomedicine – known as the Bioethics Convention Oviedo. Its main purpose is to protect individuals against exploitation.

10.2 Recruitment and consent

See also 7.3.1 Recruitment and sampling

Recruitment

Subjects will first be informed about the GRIP study through an e-mail they receive from the study coordinator of the study in which they already participate. In this e-mail, we will link to the Patient Information Form of the GRIP study. By filling out the questionnaire in Formdesk, the subjects consent for sharing their home address, phone number and e-mail address with us, so we can contact them about participation in the GRIP study.

Information

After receiving the contact information, the GRIP study team will contact potential participants by phone to inform them about the GRIP study, answer the questions the subjects might have and collect additional data. This team consists of the principal investigator, the research coordinator of the departmental Trialbureau and a research supporter.

Consent

If the subject is interested in participating in the GRIP study, the GRIP study team will send the subject the saliva collection kit and an informed consent form with a retour envelop. Only when we receive a completely signed consent form, the subject participates in the GRIP study. If, after several reminders, we do not receive a signed informed consent form, we will destroy all data that we have collected in the phone call.

Time path

We expect to be able to call the subject within one week after receiving their contact details. We expect to be able to send the collection kit and consent form within one week after the phone call. These two weeks between first contact and signing the informed consent form are ample time for subjects to consider their participation.

10.3 Objection by minors or incapacitated subjects (if applicable)

The research will be conducted according to the Code of Conduct for Medical Research by the Federation of Dutch Medical Scientific Societies (Federa) and the code of conduct relating to expressions of objection by minors participating in medical research by the Netherlands Association for pediatric research.

<https://www.ccmo.nl/onderzoekers/publicaties/publicaties/2001/06/01/gedragscodeverzet-bii-minderiarigen>

<https://english.ccmo.nl/investigators/legal-framework-for-medical-scientificresearch/codes-of-conduct/code-of-conduct-for-medical-research>

10.4 Benefits and risks assessment, group relatedness

Children with MIS-C or 'post-COVID condition' may benefit from this study since they might receive a genetic diagnosis that explains why they have had a complicated clinical course following infection with SARS-CoV-2. This may benefit them by ensuring they will receive proper care targeted at the underlying condition. At the same time, there is a risk that the genetic diagnosis does not have therapeutic consequences. This may be a burden for the participant/family. Also, a genetic diagnosis in the participant may have implications for other family members.

Controls do not benefit personally from study participation.

The procedure to collect the DNA (saliva collection) will have negligible risks and minimal burden .

This study can only be performed in minors, as it will provide age-specific data that cannot be obtained otherwise. MIS-C is a condition that mainly occurs in children (MIS-A in adults is very rare).

Regarding children with post-COVID condition: Since the immunological and clinical response to SARS-CoV-2 is markedly different between adults and children, results obtained in studies on post-COVID condition or 'long COVID' in adults do not automatically apply to children with this condition.

10.5 Compensation for injury

The sponsor/investigator has a liability insurance which is in accordance with article 7 of the WMO. We request dispensation by the METC for the statutory obligation to provide insurance for damage to research subjects, because participating in this study is without risks.

10.6 Incentives (if applicable)

Not applicable.

11. ADMINISTRATIVE ASPECTS, MONITORING AND PUBLICATION

11.1 Handling and storage of data and documents

Participants will receive a GRIP study number. The key to the code is safeguarded by the research team at the local site, by placing this in a secured datasafe managed by the 'Trialbureau' of the 'Willem-Alexander Kinderziekenhuis' (WAKZ).

Documentation belonging to the study will be archived for 15 years in the "Investigator File". Signed informed consent forms will be stored in a secured physical location in the LUMC. Biological material will be labelled with the GRIP study number and date of sampling. Clinical information of healthy controls will be collected using Castor EDC. Castor EDC is a LUMC approved data storage program.

During the study, within the LUMC [name] and the research supporter will have access to both coded and source data. After completion of the study, the key to the code will be safeguarded with the Trialbureau WAKZ, an independent location. The LUMC GRIP team won't have access to the key to the code when analyzing the collected data.

We will ask the patients or their caregivers for consent to request information regarding the clinical information collected in the existing studies on MIS-C or 'post-COVID condition'. We will link the GRIP study number to the clinical data using a unique identifier in the recruitment email.

Biological samples will be stored for 15 years for additional investigations that are related to this study. As soon as the samples are no longer necessary, the material will be destroyed.

11.2 Monitoring and Quality Assurance

Monitoring will be executed by (internal) monitors of the LUMC according to the monitor plan.

11.3 Amendments

Amendments are changes made to the research after a favourable opinion by the accredited METC has been given. All amendments will be notified to the METC that gave a favourable opinion.

Non-substantial amendments will not be notified to the accredited METC and the competent authority, but will be recorded and filed by the sponsor.

11.4 Annual progress report

The sponsor/investigator will submit a summary of the progress of the trial to the accredited METC once a year. Information will be provided on the date of inclusion of the first subject, numbers of subjects included and numbers of subjects that have completed the trial, serious adverse events, other problems, and amendments.

11.5 Temporary halt and (prematurely) end of study report

The investigator/sponsor will notify the accredited METC of the end of the study within a period of 8 weeks. The end of the study is defined as receiving the results of the DNA analyses of the last included participant.

The sponsor will notify the METC immediately of a temporary halt of the study, including the reason of such an action.

In case the study is ended prematurely, the sponsor will notify the accredited METC within 15 days, including the reasons for the premature termination.

Within one year after the end of the study, the investigator/sponsor will submit a final study report with the results of the study, including any publications/abstracts of the study, to the accredited METC.

11.6 Public disclosure and publication policy

The results of this study will be published in peer-reviewed journals, initiated by the sponsor. Preliminary results will be published on a dashboard on the website www.covidkids.nl. The investigators of the participating sites of the COPP-study will form part of the publishing consortium.

12. STRUCTURED RISK ANALYSIS

12.1 Potential issues of concern

For the assisted collection kit (with a sponge to collect saliva): As per manufacturer guidance, we will instruct the parents/caregivers to check the sponge for damage each time before inserting into donor's mouth. Use second sponge if first sponge shows any signs of wear or tear.

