GRIP Saliva Collection Kit

When a subject want to participate in the GRIP study, we will send the 'GRIP Saliva Collection Kit' to their home address. This package will contain the following materials:

- A Saliva collection kit
- A manual on how to use the kit and where to find additional information (using a QR code and a link to refer them to the instruction video), see also **Appendix A**.
- The consent form that parents and/or children need to sign to participate in the GRIP study
- A return envelope

Children under the age of four years will receive a saliva collection kit for assisted collection, which contains an absorbant sponge. Sample saliva volume for this kit is 0.75 mL.

- advantage of the assisted collection kit: ideal if the donor is not able to spit
- disadvantages of the assisted collection kit: longer collection time (it may take up to 15 minutes to collect enough saliva); more expensive; DNA yield is lower (median yield 17.3 µg)

For children over the age of four years, we will provide a collection kit for self-collection of saliva. Children will need to spit into a funnel to collect the saliva. Sample saliva volume for this kit is 2 mL.

- advantages of the self-collection kit: shorter collection time (2-5 minutes), less expensive, higher DNA yield (median yield 110 µg)
- disadvantage of the self-collection kit: the participant needs to be able to spit into the funnel until the fill line is reached

In the introductory phone call, we will ask the parents of children over the age of four years if they think their child is able to spit into the funnel. If not, the parents/participant will receive the assisted-collection kit.

When the subject has returned the collected saliva and a completely signed consent form, he or she is officially a participant in the GRIP study.

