8.2.2 Serious adverse events (SAEs)

A serious adverse event is any untoward medical occurrence or effect that

- results in death;
- is life threatening (at the time of the event);
- requires hospitalization or prolongation of existing inpatients' hospitalization;
- results in persistent or significant disability or incapacity;
- is a congenital anomaly or birth defect; or
- any other important medical event that did not result in any of the outcomes listed above due to medical or surgical intervention but could have been based upon appropriate judgement by the investigator.

An elective hospital admission will not be considered as a serious adverse event.

Only study related SAE's will be reported immediately. This means all SAE's related to participation in this study protocol, meaning from the saliva collection, will be reported. All other SAE's will not be reported, since the study procedure is considered to be of very low risk.

The sponsor will report these SAEs through the web portal ToetsingOnline to the accredited METC that approved the protocol, within 7 days of first knowledge for SAEs that result in death or are life threatening followed by a period of maximum of 8 days to complete the initial preliminary report. All other SAEs will be reported within a period of maximum 15 days after the sponsor has first knowledge of the serious adverse events.

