- Let op: Uw kind mag 30 minuten voor het afnemen van het speeksel niet eten of drinken.
- Uw kind moet tijdens de afname rechtop zitten.
- Zorg ervoor dat u de plastic folie op het bovenste gedeelte van het buisje ("de trechter") **NIET** verwijdert.
- Het kan ongeveer 15 minuten duren om het speeksel af te nemen. Zorg ervoor dat u rustig de tijd neemt om het speeksel af te nemen.

Volg de stappen in de instructievideo zo goed mogelijk:

[figure not shown]
1.	Plaats de spons binnenin de wang. Beweeg de spons gedurende 30 seconde voorzichtig langs het tandvlees en de binnenkant van de wangen om zoveel mogelijk speeksel op te nemen.	
2.	Zodra de spons vol zit met speeksel, plaatst u de spons in de V-inkeping (V-notch) van de trechter. Om het speeksel in het buisje te verzamelen, moet u de spons met een draaiende en duwende beweging tegen de binnenkant van de V-inkeping houden.	
3.	Herhaal stap 1 en stap 2 met hetzelfde sponsje totdat het speeksel tot het streepje op het buisje komt ("Fill line"). Zorg ervoor dat er zo min mogelijk belletjes in het speeksel zitten. Het is belangrijk om te controleren of de spons kapot gaat. Als de spons kapot gaat moet u een tweede spons gebruiken om verder te gaan met de speekselverzameling.	
4.	Als er genoeg speeksel in het buisje zit, sluit u de deksel door er stevig op te drukken. Als u een harde klik hoort zit het goed dicht. Zorg ervoor dat u het buisje rechtop houdt en dat de deksel goed gesloten is.	
5.	Schroef het bovenste gedeelte ("de trechter") los van het buisje.	
6.	Sluit het buisje door de kleine dop stevig op het buisje te draaien.	
7.	Schud het buisje met het dopje erop gedurende 5 seconde. Gooi het bovenste gedeelte ("de trechter") in de vuilnisbak. Ook het gebruikte sponsje of de gebruikte sponsjes kunt u weggooien.	

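### The parent instruction in Appendix A 14.1 gives a looser sponge check than section 12.1 promises: none before the first insertion, no stated timing afterwards, and a narrower reason to replace the sponge

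*Protocol*

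**What the plan says.** Section 12.1 deals with a single issue, the sponge in the assisted collection kit. Citing the manufacturer's guidance, it commits the study to a particular instruction: "we will instruct the parents/caregivers to check the sponge for damage each time before inserting into donor's mouth". The rule for replacement follows: "Use second sponge if first sponge shows any signs of wear or tear". Section 12.2 then concludes that the risk of the kits is negligible, on condition that they are used properly.

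Section 7.3.1 says who gets the sponge: "Children under the age of four years will receive a saliva collection kit for assisted collection, which contains an absorbant sponge". Older children who cannot spit into the funnel get the same kit. The package sent to the home contains a manual, which section 7.3.1 links to Appendix A and describes as pointing parents to further material, "using a QR code and a link to refer them to the instruction video".

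Appendix A 14.1 is the written instruction for the assisted kit. Its step 1 begins: "Plaats de spons binnenin de wang. Beweeg de spons gedurende 30 seconde voorzichtig langs het tandvlees en de binnenkant van de wangen". Step 2 has the parent twist and press the sponge against the notch of the funnel. Step 3 opens with "Herhaal stap 1 en stap 2 met hetzelfde sponsje", to be continued until the tube is filled to the line, and adds: "Het is belangrijk om te controleren of de spons kapot gaat. Als de spons kapot gaat moet u een tweede spons gebruiken".

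**The concern.** Two current parts of one protocol describe the same instruction differently. Section 12.1 says what parents will be told; Appendix A 14.1 is what the written sheet tells them. A parent who works from the sheet is not asked to look at the sponge before it first goes into the child's mouth. The parent is also not told to look before each later insertion, or to change the sponge at the first sign of wear.

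The gap concerns participant safety and not inference. It deserves correction because the safeguard is the only one offered for the only concern listed, and the conclusion in section 12.2 depends on it. Section 10.5 also asks the ethics committee for dispensation from subject insurance on the ground that taking part carries no risk. Collection is done at home by parents, largely from very young children. Section 8.2.1 says adverse events will not be registered. Section 8.2.2 does cover serious ones: "all SAE's related to participation in this study protocol, meaning from the saliva collection, will be reported". A non-serious sponge incident would therefore leave no record, and the instruction is the main protection.

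**Working it through.** The plan gives no figure on this point and no arithmetic applies beyond a count. The check is a comparison of section 12.1 with Appendix A 14.1.

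| Element | Section 12.1 | Appendix A 14.1 |
|---|---|---|
| Check before the first insertion | Yes, since the check applies every time | None: not in the four preparatory bullets, not in step 1 |
| Check before later insertions | Yes, every time | Step 3 asks for a check but does not say when or how often |
| When to change the sponge | Any sign of wear or tear | When it *kapot gaat* (breaks or is breaking) |
| Second sponge | Yes | Yes, step 3 |

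**Count.** The four preparatory bullets cover eating and drinking, sitting upright, leaving the plastic film in place, and taking enough time. A sponge check appears in 0 of these 4. Of the 7 numbered steps, 1 contains a check (step 3). Steps 4 to 7 cover closing, unscrewing, capping and shaking the tube, when the sponge is no longer in use. The fair denominator is therefore steps 1 to 3, of which 1 in 3 has the check. Step 1, which inserts the sponge, does not.

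**Sequence.** Followed literally, the sheet runs: insert (step 1), squeeze (step 2), then return to steps 1 and 2 with the same sponge (step 3). Because step 1 has no check, repeating it brings none. The check in step 3 stands beside the instruction to repeat, so it can be read as falling between squeezing and re-insertion, but the text does not say so. On any reading it comes after the first insertion.

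**Other routes to parents.** The telephone call described in section 7.3.1 covers the explanation of the study, questions, eligibility of controls, family origin and the choice of kit. A sponge check is not among the listed items. The video is referred to, but its content is not in the protocol.

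**Result.** There are three differences: no check before first use, no timing for the later check, and a narrower trigger for replacement.

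**The case against.** The strongest reply is that the two texts do not conflict. Section 12.1 has two components, checking for damage and replacing a damaged sponge, and both are in step 3. Nothing in the sheet tells a parent to do what section 12.1 rules out. The check also sits where it matters most, after the sponge has been twisted and pressed and before it goes back into the mouth. What is left uncovered is the first insertion, when the sponge is unused. *Kapot gaat* describes a process and is everyday Dutch for something that is getting damaged, which is close to wear or tear. Finally, section 12.1 does not say that the instruction is given only through Appendix A. The sheet tells parents to follow the video, and the video and figures cannot be seen here.

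Much of this stands, and it limits the weight of the point. Some checking between insertions is implied, the difference in trigger is one of degree, and the full instruction may be in the video. It does not remove the mismatch. Section 12.1 requires the check every time, which includes the first, and the written sheet has nothing there. Nor is breaking, even when under way, the same as any sign of wear. If the video does contain the full check, parents receive two versions, and the printed one is the weaker.

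**Conclusion.** The point holds as a minor inconsistency within the protocol. The written instruction is looser than the safeguard in section 12.1 in three respects: first insertion, timing and trigger. It concerns only children given the assisted kit. The protocol does not say how many these are, and no probability of harm can be derived from it. Sample collection, data and analysis are unaffected.

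Confidence is high for the printed text. The conclusion rests on Appendix A 14.1 being the written instruction in the kit, as the cross-reference in section 7.3.1 indicates. It makes no claim about the video or the figures. The manufacturer's guidance is known here only through the description in section 12.1.

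**What to change.** In Appendix A 14.1:

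- Open step 1 with an instruction to check the sponge for damage before each insertion. Since step 3 sends the parent back to step 1, the check then recurs by itself.
- In step 3, change the reason for taking the second sponge from breaking to any sign of wear or tear.
- Confirm that the instruction video gives the same check and the same trigger.

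The cost is about two sentences in the Dutch parent sheet and one viewing of the video. The instruction for self-collection in 14.2 uses no sponge and needs no change.

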12.2 Synthesis

With proper use, there is a negligible risk to use the saliva collection kits.

- Let op: Uw kind mag 30 minuten voor het afnemen van het speeksel niet eten of drinken.
- Uw kind moet tijdens de afname rechtop zitten.
- Zorg ervoor dat u de plastic folie op het bovenste gedeelte van het buisje ("de trechter") **NIET** verwijdert.
- Het kan ongeveer 15 minuten duren om het speeksel af te nemen. Zorg ervoor dat u rustig de tijd neemt om het speeksel af te nemen.

Volg de stappen in de instructievideo zo goed mogelijk:

[figure not shown]
1.	Plaats de spons binnenin de wang. Beweeg de spons gedurende 30 seconde voorzichtig langs het tandvlees en de binnenkant van de wangen om zoveel mogelijk speeksel op te nemen.	
2.	Zodra de spons vol zit met speeksel, plaatst u de spons in de V-inkeping (V-notch) van de trechter. Om het speeksel in het buisje te verzamelen, moet u de spons met een draaiende en duwende beweging tegen de binnenkant van de V-inkeping houden.	
3.	Herhaal stap 1 en stap 2 met hetzelfde sponsje totdat het speeksel tot het streepje op het buisje komt ("Fill line"). Zorg ervoor dat er zo min mogelijk belletjes in het speeksel zitten. Het is belangrijk om te controleren of de spons kapot gaat. Als de spons kapot gaat moet u een tweede spons gebruiken om verder te gaan met de speekselverzameling.	
4.	Als er genoeg speeksel in het buisje zit, sluit u de deksel door er stevig op te drukken. Als u een harde klik hoort zit het goed dicht. Zorg ervoor dat u het buisje rechtop houdt en dat de deksel goed gesloten is.	
5.	Schroef het bovenste gedeelte ("de trechter") los van het buisje.	
6.	Sluit het buisje door de kleine dop stevig op het buisje te draaien.	
7.	Schud het buisje met het dopje erop gedurende 5 seconde. Gooi het bovenste gedeelte ("de trechter") in de vuilnisbak. Ook het gebruikte sponsje of de gebruikte sponsjes kunt u weggooien.	

